11.4. Clinician's Global Aesthetic Improvement Scale (CGAIS)

Subjective assessment of aesthetic improvement will be performed at 3-months and 6-months post-treatment (See Appendix IV).

The scale should be completed in two steps:

- 1 Based on a live assessment of the subject while referring to the subject's pre-treatment photographs of the face and neck, and
- 2 Based on a comparison of the subject's pre-treatment photographs to the current post-treatment photographs of the face and neck.

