Two 0.33 mm punch biopsies will be taken from the cheek adjacent to the lateral upper lip at Visit 2, Visit 6 and Visit 7. Prior to biopsy the area will be cleaned with alcohol and a local numbing agent, 0.5%-1% Lidocaine with epinephrine, will be used to anesthetize the area being biopsied. If bleeding is present, pressure will be held on the biopsy site until bleeding stops. Immediately after collection, biopsies for histology and gene expression will be put in 4% PFA and RNA-Later solution, respectively. Biopsies will be stored in a cooler for transfer to the Plastic Surgery Research Lab at UTSW for molecular analysis.

11.10. *Blinded Evaluation*

Blinded evaluation will be performed by three qualified, non-treating clinicians to determine if the InMode Morpheus8 System is effective in improving the appearance of facial and neck skin quality and dermal lines.

At study conclusion, the Principal Investigator will select three blinded, physician evaluators to assess photos of subjects taken pre- and post-treatment. The evaluators will be trained

by the PI or research team member on the grading scales in order to independently review photographs for each subject. The evaluators will be blinded to subject information and will only know that the study consisted of multiple treatment visits and follow up visits at 3 months and 6 months. They will be provided a set of photos taken at three different visits – pre-treatment, 3 month post-treatment and 6 month post-treatment – in a randomized and unidentifiable order. No information will be provided that may allow them to determine the baseline from follow up imaging. Evaluators will be asked to assess the sets of pictures using the Lemperle Wrinkle, Allergan Fine Lines and Allergan Skin Roughness scales. After completion of the scales, the raters will be unblinded and asked to complete the Clinical Global Aesthetics Improved Scale (CGAIS).

The source documents will be prepared and distributed to the blinded evaluators by a member of the study staff. A decreased score for each assessment will indicate an improvement for the indicated parameters.

12. Statistical Methods of Analysis

This initial study will include change from baseline analysis.

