The primary outcome measure of effectiveness will be a paired comparison of baseline to all applicable post-baseline time points using data obtained from transepidermal water loss assessments, high resolution ultrasonography, BTC 2000 measurements, biopsy results, and 3D imaging results. Photographs and 3D video of treated skin at follow-up visits will be compared to baseline for blinded scoring evaluations. Mean of the change from baseline (defined as post-baseline value minus baseline value) will be estimated at post-baseline time points for applicable parameters.

The following will be calculated and reported for each evaluation parameter at the applicable post-baseline time point(s):

$$\text{Percent mean change from baseline} = \frac{\text{(visit mean score} - \text{baseline mean score})}{\text{baseline mean score}} \times 100$$

For Clinician's Global Aesthetic Improvement Assessment, the null hypothesis that the mean score is equal to 4 (no change) will be tested.

13. Non-Significant Risk Determination

In accordance with the definition of "Significant Risk Device" provided in the U.S. Code of Federal Regulations 21 CFR 812.3, the study device to be used in this research study has been determined to be a Non-Significant Risk (NSR) device based on the following:

- a) It is not an implant

- b) It is not purported or represented to be for use in supporting or sustaining human life and do not present a potential for serious risk to the health, safety or welfare of a subject
- c) It is not for a use of substantial importance in diagnosing, curing, mitigating, or treating disease or otherwise preventing impairment of human health
- d) Use of the device poses no risk to the health, safety, or welfare of a subject

14. Device Description

The InMode Morpheus8 System is a minimally invasive bipolar radiofrequency (RF) microneedling device FDA-cleared for full-body adipose tissue remodeling. The fractional RF device, with adjustable penetration depth and energy delivery, contains 12-24 coated needles. During treatment, these needles penetrate and deliver thermal energy into the subdermal tissue, leading to coagulation of fat and contraction of the reticular dermis and surrounding connective tissue. Additionally, it is theorized that the thermal injury caused by the RF energy initiates the wound healing process, stimulating neocollagenesis, elastogenesis, and angiogenesis.

[figure not shown]
Image 1. InMode Morpheus8 System

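### CGAIS is a primary endpoint with the only written null hypothesis, but every CGAIS rating described is made knowing which image is pre-treatment; report it as open-label and rest efficacy on the masked scale scores

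*Combined protocol and SAP*

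**What the plan says.** Section 3 describes a single-center, unblinded, uncontrolled study of up to 13 subjects. It assigns the clinic assessments to one unblinded clinician and adds the GAIS at 3 and 6 months. Section 6.1 lists CGAIS at those two months as primary endpoint 2.

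Three kinds of CGAIS rating are described:

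- Section 11.4: "The scale should be completed in two steps". The first is "Based on a live assessment of the subject while referring to the subject's pre-treatment photographs of the face and neck".
- The second step in Section 11.4 compares pre-treatment with current photographs, again identified as such.
- Section 11.10, for the three photo raters: "After completion of the scales, the raters will be unblinded and asked to complete the Clinical Global Aesthetics Improved Scale (CGAIS".

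Before that unblinding, the same three raters do masked work. The photographs from the three visits come "in a randomized and unidentifiable order", and "Evaluators will be asked to assess the sets of pictures using the Lemperle Wrinkle, Allergan Fine Lines and Allergan Skin Roughness scales". These are the scales of primary endpoint 1.

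For CGAIS, Section 12 says that "the null hypothesis that the mean score is equal to 4 (no change) will be tested". For other parameters the mean change "will be estimated at post-baseline time points for applicable parameters", with no null hypothesis written out. Section 12 also states: "The primary outcome measure of effectiveness will be a paired comparison of baseline to all applicable post-baseline time points". That comparison uses transepidermal water loss (TEWL), ultrasound, BTC 2000, biopsy and 3D imaging.

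**The concern.** A fixed null of 4 assumes that, if the treatment does nothing, ratings will center on no change. That is doubtful when the rater knows which image came first and that treatment followed. A modest tendency to see improvement moves the mean below 4, and there is no control arm in which the same tendency would show and cancel.

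The plan masks visit order for the static scales, then lifts the mask just before the one measure that has a written null hypothesis. Because the raters' CGAIS sits in the section on blinded evaluation, a reader of the results could also take it for a blinded rating. If CGAIS is read as primary, as Section 6.1 says, a significant result would be credited to the device when part or all of it could be expectation.

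The visible text does not say which CGAIS rating enters the test (clinician or photo raters, live or photographic step), or at which month. Redacted sections may say.

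**Working it through.** **Is any CGAIS rating masked?**

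| Rating | Rater | Pre-treatment image known? |
|---|---|---|
| Section 11.4, step 1 (live) | Site clinician, unblinded (Section 3) | Yes |
| Section 11.4, step 2 (photographs) | Same | Yes |
| Section 11.10, photo raters | Three non-treating physicians, after unblinding | Yes |

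None is masked. (Section 11.4 does not itself name the rater; Section 3 is the natural source.)

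**How sensitive is the test of mean = 4?** The plan gives no test, alpha or bias rate, so there is no plan figure to reproduce. Inputs from the documents: n = 13 (the cap in Section 3), null mean 4, and grades 3 = 'Improved', 4 = 'No Change', 5 = 'Worse' (Appendix IV). Assumptions: one score per subject, nobody truly changed, two-sided 0.05, grades 1 and 2 unused.

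With k grades of 3 and the rest 4, the one-sample t statistic reduces to t = −√(12k/(13 − k)) on 12 df.

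- k = 3: t = −√(36/10) = −1.90, p = 0.082.
- k = 4: t = −√(48/9) = −2.31, p = 0.040.

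So four 'Improved' and nine 'No Change' already reject. If each subject is graded 'Improved' with probability q through expectation alone and never 'Worse', the chance of a result favouring the device is P(X ≥ 4) for X ~ Binomial(13, q). With 'Worse' grades at rate w, the trinomial probabilities are summed over all outcomes with p ≤ 0.05 in the device's favour. The exact sign test drops the 'No Change' grades; its smallest winning result is 6 of 6 (p = 2 × 0.5⁶ = 0.031).

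| 'Improved' q | t test, w = 0 | t test, w = 10% | sign test, w = 0 | sign test, w = 10% |
|---|---|---|---|---|
| 10% | 3% | 1% | 0.1% | 0.04% |
| 20% | 25% | 8% | 3% | 1% |
| 30% | 58% | 20% | 17% | 7% |
| 40% | 83% | 32% | 43% | 18% |

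The intended rate in that direction is 2.5%. If order were masked and the same share of non-tied grades split evenly, the t test would favour the device in 1 to 3% of trials for q = 20 to 40%, and the sign test in under 1%.

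**Do three raters cure it?** If the score is the majority of three independent raters and w = 0, the subject-level rate is q³ + 3q²(1 − q) = 0.104, 0.216 and 0.352 for q = 20, 30 and 40%. The t test then favours the device in 4, 30 and 73% of trials, and the sign test in 0.1, 4 and 29%. Expectation shared between raters moves these back toward the single-rater figures.

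**The case against.** The order of work in Section 11.10 looks deliberate and is partly right. GAIS grades refer to the original condition, so the scale cannot be completed without knowing the baseline image. Scoring the static scales first and unblinding afterwards protects those scales. The documents are open about the unblinded design and the unblinding step, and this is described as an initial study. All of that stands, and it limits the point to the global rating.

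A reader might infer more, in three ways that the documents do not support.

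- That the trial has no masked efficacy evidence. It has: all three scales of primary endpoint 1 are scored with visit order concealed, and Section 12 includes blinded scoring.
- That the CGAIS test is the only test planned. It carries the only written null hypothesis in the visible text, but Section 12 also plans paired comparisons of the instrument, biopsy and 3D imaging data, which would ordinarily be tested.
- That a masked global rating is required. It would be a new, coarser endpoint overlapping scores just given, and statisticians could differ on its worth.

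It is also fair to say that the large error rates depend on assumption. The 58% and 83% figures need a t test, no 'Worse' grades, and 30 to 40% of unchanged faces graded as obviously improved. They show that the test can be badly misled, not that it will be.

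**Conclusion.** The point holds in this limited form. In the visible text a primary endpoint with the only written null hypothesis rests wholly on ratings made with the pre-treatment image known, and there is no control arm. Rejecting a mean of 4 therefore cannot by itself be read as a treatment effect.

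The size of the bias is unknown. Under the assumed rates of 20 to 40% expectation-driven 'Improved' grades, the chance of a false result for the device runs from 1% (sign test, 20% 'Improved', 10% 'Worse') to 83% (t test, 40% 'Improved', no 'Worse'); at 10% 'Improved' it is small throughout.

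The documents do not support the conclusion that efficacy cannot be judged. Masked scores for lines, wrinkles and roughness are already planned and only need to be given the leading role. At present that role is unclear: Section 12 gives the primary effectiveness label to a set of measures that Section 6.1 does not contain, and Section 6.2 lists four of the five (TEWL, ultrasound, BTC 2000 and biopsy) as secondary.

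**What to change.** 1. In Section 6.1 and Section 12, report CGAIS as an open-label descriptive result, state whose rating it is, and do not use the test of mean = 4 alone as evidence of efficacy.
2. Rest the efficacy conclusion on the masked Lemperle, Fine Lines and Skin Roughness scores from Section 11.10, not on the unblinded clinician's scores on the same scales. Give change from baseline with a 95% CI at one month named in advance. Combine the three raters into one score per subject (for example the mean or median), since three raters on 13 subjects are not 39 independent observations. Name the lower-face Lemperle regions that count, because Appendix I also lists areas such as the forehead. Say how the three scales are to be read together.
3. Reconcile the primary effectiveness measure in Section 12 with Sections 6.1 and 6.2.

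These are wording changes on data already planned. The price is a probably less favourable result.

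Optional: before unblinding, the same raters judge pairs of the same photographs (A better, B better, no difference) in concealed order. Analyse this as supportive, by exact sign test on the subject-level majority. It costs one short form, is coarser than GAIS and partly repeats the scale scores. At assumed subject-level majority rates of 60% improved and 10% worse, power is about 50% with 13 subjects and 33% with 10 evaluable.

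Masking does not remove regression to the mean, natural change or differences in photographic conditions, and the report should say so.

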Clinical Assessment of Skin Quality and Efficacy of Dermal Line Improvement Following Four Bipolar Radiofrequency Microneedling Treatments

NCT 05085730

Document Date: 11/17/2022

Clinical Assessment of Skin Quality and Efficacy of Dermal Line Improvement Following Four Bipolar Radiofrequency Microneedling Treatments

[REDACTED]	[REDACTED]
[REDACTED]	[REDACTED]
PRINCIPAL INVESTIGATOR	[name], MD
SUB-INVESTIGATORS	[name], MD [name], MBe

[REDACTED]

[REDACTED]

[REDACTED]

[REDACTED]

[REDACTED]

[REDACTED]

[REDACTED]

[REDACTED]

2. Purpose

The primary objective of this study is to evaluate the safety and efficacy of a bipolar fractional radiofrequency treatment via use of the InMode Morpheus8 System to achieve skin texture and quality change and to treat facial fine lines and wrinkles of the lower face.

[figure not shown]
3. Study Design

This is a single center, unblinded, non-randomized, non-controlled study designed to follow a total of up to thirteen (13) qualified and consenting subjects receiving 4 bipolar fractional radiofrequency microneedling treatment of the lower face, once every 4-6 weeks for a total of 4 treatments, under an IRB approved protocol. Following these treatments, patients will have follow-up visits at 3-months, and 6-months post-treatment. The effects of bipolar fractional radiofrequency treatments via the InMode Morpheus8 System will be determined by subjective and objective analysis through clinician and subject assessments.

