5.1. Inclusion Criteria

- 1 Healthy male and female adults between ages 21-70 years of age.
- 2 Presence of facial dermal lines and skin changes of the lower face associated with age or environmental exposure.
- 3 Subjects who can read, understand, and sign the Informed Consent Form.
- 4 Subjects willing and able to comply with all study requirements.
- 5 Fitzpatrick skin type I-VI.
- 6 Minimum of 1 on the Lemperle Wrinkle Assessment Scale, Allergan Fine Line Scale and Allergan Skin Roughness Scale
- 7 Subject is willing not to undergo any type of aesthetic procedure that could confound the study device treatment effects until he/she completes the study.

5.2. Exclusion Criteria:

- 1 Active localized or systemic infections, that may alter wound healing.
- 2 Immunocompromised subjects.
- 3 Subjects with coagulation disorder.
- 4 History of skin photosensitivity disorders, or use of photosensitizing drugs (e.g., tetracycline or sulfa drugs).
- 5 Pregnant and/or lactating (All female volunteers will be advised about using birth control during the period of study).
- 6 5 on the Lemperle Wrinkle Assessment Scale or 4 on the Allergan Fine Line Scale and/or Allergan Skin Roughness Scales
- 7 Scarring in areas to be treated.
- 8 Tattoos in the treatment areas to be treated.
- 9 Significant open facial wounds or lesions.
- 10 Severe or cystic acne in treatment areas.
- 11 Current active smoker.
- 12 Use of Accutane (Isotretinoin) within the past 6 months.
- 13 Use of topical retinoids within 48 hours.
- 14 Use of prescription anticoagulants.
- 15 Pacemaker or internal defibrillator.
- 16 History of skin disorders resulting in abnormal wound healing (i.e. keloids, extreme dry and fragile skin).
- 17 Subjects on current oral corticosteroid therapy or within the past 6 months
- 18 Metal implants in the treatment area.
- 19 In the opinion of the investigator, subject is unwilling or unable to adhere to all study requirements, including application and follow-up visits.
- 20 Subjects with a history of radiation therapy to the treatment area.
- 21 Subject has a history of allergy to lidocaine or ester-based local anesthetics.
- 22 Subjects with significant cardiac history or rhythm disturbance who may be unable to tolerate lidocaine with epinephrine.

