6.1. Primary Endpoints

- 1 Improvement of fine lines and wrinkle severity using a modified Lemperle Wrinkle Assessment Scale, the Allergan Scale for Fine Lines and the Allergan Skin Roughness Scale Assessment at baseline, 3-months, and 6-months post-treatment
- 2 Clinician's Global Aesthetic Improvement Scale (CGAIS) at 3-months and 6-months post-treatment

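### Can the Section 12 percent-change formula show a change on the Lemperle and Allergan scales when no subject has changed?

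*Combined protocol and SAP*

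**What the plan says.** Section 12 (Statistical Methods of Analysis) announces an analysis of change from baseline and then gives three relevant elements.

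- A paired comparison for the instrument, biopsy and 3D imaging data: "paired comparison of baseline to all applicable post-baseline time points using data obtained from transepidermal water loss assessments", followed by ultrasound, BTC 2000, biopsy and 3D imaging. The next sentence adds that follow-up photographs and 3D video are set against baseline for the blinded scoring.
- A mean change: "Mean of the change from baseline (defined as post-baseline value minus baseline value) will be estimated at post-baseline time points".
- A percent change, introduced by "The following will be calculated and reported for each evaluation parameter at the applicable post-baseline time point(s", equal to visit mean less baseline mean, over baseline mean, times 100.

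The clinician's GAIS has its own analysis: "the null hypothesis that the mean score is equal to 4 (no change) will be tested".

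The wrinkle, fine-line and roughness scales are primary in Section 6.1: "Improvement of fine lines and wrinkle severity using a modified Lemperle Wrinkle Assessment Scale", together with the two Allergan scales. Section 3 plans for "up to thirteen (13) qualified and consenting subjects". The visible text has no rule for missed visits, but blocks are redacted before Section 10 and between Sections 17 and 21.

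**The concern.** The percent change is written as a ratio built from two group means, and nothing beside it says who belongs to each group. Taken literally, the baseline mean could cover all enrolled subjects and the visit mean only those who attended. The two means then describe different people, and the percentage mixes real change with the make-up of the remaining group.

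Several features make this look serious. The sample is at most 13, so each absent subject carries weight. There is no control arm in which the artefact would also appear. Section 11.10 treats a lower score as improvement, so losing the more severe subjects would look like benefit. The sentence that uses the word paired does not list the Lemperle or Allergan scales. The percentage is one of only two summaries that Section 12 gives for those scales. The last visit falls about 9 to 10 months after the first treatment (three gaps of 4 to 6 weeks, then 6 months), so some missed visits are plausible.

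A smaller point is that the formula is prescribed for every parameter, while the subject GAIS and the satisfaction questionnaire have no baseline.

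**Working it through.** The plan states no expected percent change, so there is no figure to reproduce. The check has two parts: what the formula gives under each reading, and how large the gap could be.

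**The two readings.** Let S be the subjects seen at a visit, x the baseline score and y the visit score.

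- Both means over S: 100 × (mean of y in S − mean of x in S) / mean of x in S. Because the same people are in both means, this equals 100 × (mean of y − x in S) / mean of x in S. It is the percentage form of the mean change that Section 12 has just defined, and it is 0 whenever nobody changes.
- Baseline mean over all enrolled: the numerator becomes (mean of y − x in S) + (mean of x in S − mean of x in all). The second bracket is the artefact. It is 0 with complete follow-up, with equal baselines, or when those lost have the same mean grade as those who stay.

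**Inputs for the size.**

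- n = 13, the maximum in Section 3.
- Permitted baseline grades: at least 1 on each scale (Section 5.1), and Section 5.2 excludes "5 on the Lemperle Wrinkle Assessment Scale or 4 on the Allergan Fine Line Scale and/or Allergan Skin Roughness Scales". In whole grades this leaves 1 to 4 for Lemperle and 1 to 3 for the Allergan scales.
- Assumed, because the documents give neither: the baseline distribution and 1 to 3 missing subjects.

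**Set A (allowed on all three scales): four 1s, five 2s, four 3s.** The sum is 26 and the mean 26/13 = 2.00. No subject changes.

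- Lose one 3: 23/12 = 1.917, and (1.917 − 2.00)/2.00 = −4.2%.
- Lose two 3s: 20/11 = 1.818, giving −9.1%.
- Lose three 3s: 17/10 = 1.70, giving −15.0%.
- Losing 1s instead gives +4.2%, +9.1% and +15.0%.

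All possible missing sets, each equally likely:

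| Missing | Sets | Range | Mean error | Mean absolute error | Exactly 0 | Above 5.0 points in size |
|---|---|---|---|---|---|---|
| 1 | 13 | −4.2% to +4.2% | 0 | 2.6 points | 5 (38%) | 0 |
| 2 | 78 | −9.1% to +9.1% | 0 | 3.7 points | 26 (33%) | 12 (15%) |
| 3 | 286 | −15.0% to +15.0% | 0 | 4.8 points | 90 (31%) | 68 (24%) |

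With three missing, the smallest non-zero error is exactly 5.0 points, and 128 of the 286 sets (45%) sit on that value. Counting errors of 5 points or more would therefore give 196/286 = 69%, which says only that the error is not zero. The ±15.0% ends occur in 4 of 286 sets each (1.4%).

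**Set B (Lemperle only): two 1s, five 2s, four 3s, two 4s.** The sum is 32 and the mean 2.462. With three missing, the lowest remaining mean is 2.10 (−14.7%) and the highest 2.80 (+13.8%).

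**Yardstick.** A true one-grade improvement in one of 13 subjects at mean 2.00 is (1/13)/2.00 = 3.8%.

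**Which reading the section supports.** The formula comes directly after a definition of change as each post-baseline value minus its baseline value, in a section announced as change from baseline. For the blinded ratings, Section 11.10 has each evaluator score photographs from the three visits subject by subject on these same three scales, and Section 12 compares the follow-up photographs with baseline. Nothing in the plan points to an all-enrolled baseline mean.

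**The case for a change.** The strongest case for a change is that the formula does not exclude the unmatched reading, that such a choice is better fixed before the data are seen, and that one clause would fix it at no cost to patients or data. In so small a study the artefact can rival a real effect: in Set A one lost grade-3 subject gives −4.2%, against −3.8% for one subject who truly improves by a grade. The photograph comparison states no missed-visit rule and does not cover the unblinded clinician's own ratings.

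Part of this stands. The text is silent on the point, and a clarifying clause would do no harm. But silence is not a wrong formula. An analyst reporting percent change beside a within-subject mean change would ordinarily use the same people for both. One who did not would see the two disagree, most plainly when the mean change is 0 and the percentage is not. Matching also removes only this artefact and does nothing about who was lost, which is the more substantial missing-data question. Redacted text may already hold a rule on that.

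The simulated sizes may also be too large. Section 11.1 lists eleven facial regions for Lemperle and Section 11.10 uses three raters. If scores were averaged over these, which the plan does not say, the spread between subjects, and so the artefact, could be smaller.

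The point about measures without a baseline changes no result. The formula cannot be computed for them, so nobody would be misled. The clinician's GAIS already has its own test.

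**Conclusion.** The concern is arithmetically possible, but it calls for no change. It needs three things together: missed follow-ups, a remaining group whose baseline mean differs from that of the full group, and an analyst who takes the baseline mean over everyone enrolled. The plan does not ask for the last of these, and its own definition of change points the other way. On the natural reading the error is exactly 0.

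On the unfavourable reading, with assumed Set A grades and 1, 2 or 3 of 13 missing, the average absolute discrepancy is 2.6, 3.7 or 4.8 percentage points. The signed error averages zero if loss is unrelated to baseline grade. If the more severe subjects were the ones lost, it would lean toward apparent improvement. These sizes rest on invented baseline grades and losses, because the documents give neither. The percentage is descriptive and carries no visible test, so no inference in the plan depends on it. This is a gap in wording that sensible analysis fills.

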Overall assessment of clinical outcome and safety will be based on clinic visits and evaluation of pre- and post-procedural photos. These photos will be identifiable full face photos, and subjects will be adequately informed of such. One unblinded clinician's assessments of satisfaction will be characterized using the Lemperle Wrinkle Assessment Scale, a four-point Allergan skin fine line scale and a four-point Allergan Skin Roughness scale at baseline, 3 month follow up and 6 month follow up visits. The five-point Global Aesthetic Improvement Scale (GAIS) will also be used at 3 month and 6 month follow up visits. Additionally, evaluation of pre- and post-procedural photos will be performed comparing baseline and follow ups by blinded raters. In conjunction with standard and close-up photography, subjects will also have photos taken using the VISIA Imaging system and will undergo high-resolution ultrasonography, transepidermal water loss (TEWL) measurements and/or BTC 2000 measurements for exploratory purposes. High-resolution ultrasound will be utilized for assessment of skin thickness and density. TEWL measurements are taken via the Bio Aquaflux and will be used to evaluate barrier function of the skin epidermal layer to determine progress of epidermal healing after treatment and BTC

2000 will be used to measure skin laxity, viscoelastic deformation, stiffness, energy absorption, elasticity and deformation values of skin. Additionally consenting subjects will undergo skin biopsies at the treatment site to better qualify the measurements and results from the items mentioned above. Micro-biopsies using 0.33mm size punches will be used to extract core tissues pre- and post-treatment for histological evaluation (tissue structure, elastin, collagen and hyaluronic acid expression) and gene expression assessment (elastin, other major ECM molecules and elastin related genes).

From these exploratory procedures the improvement in skin quality and dermal lines of the lower face and jawline can be evaluated in comparison to pre-treatment assessments.

5. Eligibility Criteria

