
22. Appendix

- I. Lemperle Wrinkle Assessment Scale⁹

Classification of Facial Wrinkles

Facial Wrinkle	Class	Description
Horizontal forehead lines	0	No wrinkles
Glabellar frown lines	1	Just perceptible wrinkle
Periorbital lines	2	Shallow wrinkles
Preauricular lines	3	Moderately deep wrinkle
Cheek lines	4	Deep wrinkle, well-defined edges
Nasolabial folds	5	Very deep wrinkle, redundant fold
Radial upper lip lines		
Radial lower lip lines		
Corner of the mouth lines		
Marionette lines		
Labiomental crease		
Horizontal neck folds		

II. Allergan Fine Lines Scale¹¹

a.

Grade	Term	Descriptor
0	None	No fine lines
1	Minimal	1–2 superficial lines
2	Moderate	3–5 superficial lines
3	Severe	Greater than 5 superficial lines; no crosshatching
4	Diffuse	Diffuse superficial lines; crosshatching

b.

III. Allergan Skin Roughness Scale for Evaluation of Facial Skin Texture¹³

a.

TABLE 1. Descriptors for the Allergan Skin Roughness Scale

Grade	Term	Descriptor
0	None	Smooth visual skin texture
1	Minimal	Slightly coarse and uneven visual skin texture
2	Moderate	Moderately coarse and uneven visual skin texture; may have early elastosis
3	Severe	Severely coarse visual skin texture, crosshatched fine lines; may have some elastosis
4	Extreme	Extremely coarse visual skin texture, crosshatched deep creases; extreme elastosis

b.

Allergan Skin Roughness Scale

IV. Global Aesthetic Improvement Scale (GAIS)

Rating	Description
1	Very Much Improved: Optimal cosmetic result in this subject.
2	Much Improved: Marked improvement in appearance from the initial condition, but not completely optimal for this subject.
3	Improved: Obvious improvement in appearance from initial condition, but a re-treatment is indicated.
4	No Change: The appearance is essentially the same as the original condition.
5	Worse: The appearance is worse than the original condition.

V. Patient Satisfaction Questionnaire

PATIENT SATISFACTION QUESTIONNAIRE

PLEASE HAVE THE SUBJECT COMPLETE THIS ASSESSMENT WHILE REFERRING TO BASELINE PHOTOS.

COMPARE HOW YOUR FACE CURRENTLY LOOKS WITH YOUR PRE-TREATMENT PHOTOS

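### Does the CGAIS test against a mean of 4 need the rater, visit and grade counts written into Section 12?

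*Combined protocol and SAP*

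**What the plan says.** Section 6.1 lists as its second primary endpoint the "Clinician's Global Aesthetic Improvement Scale (CGAIS) at 3-months and 6-months post-treatment". Section 3 describes "One unblinded clinician's assessments of satisfaction" on the wrinkle, fine-line and roughness scales, and adds: "The five-point Global Aesthetic Improvement Scale (GAIS) will also be used at 3 month and 6 month follow up visits". Section 11.4 says of the CGAIS: "The scale should be completed in two steps", the first a live assessment against the pre-treatment photographs and the second a comparison of photographs.

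Section 11.10 gives a scale with the same acronym to the three photo evaluators. Once they have finished the masked scales, "the raters will be unblinded and asked to complete the Clinical Global Aesthetics Improved Scale (CGAIS". It does not say whether they do this once per subject or once for each follow-up.

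In Section 12, the only sentence specific to the clinician's global scale states that "the null hypothesis that the mean score is equal to 4 (no change) will be tested". No test, alpha or sidedness is given. In Appendix IV, grades 1 to 3 are degrees of improvement, 4 is no change, and 5 is the only worsening grade: "Worse: The appearance is worse than the original condition".

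**The concern.** CGAIS is a primary endpoint and carries the only null hypothesis stated in Section 12. The plan nevertheless yields several CGAIS scores per subject and does not say in so many words which one is tested. If the rater, step or visit were settled after the data were seen, or if three panel readings on each of 13 subjects were treated as 39 independent observations, the chance of a false claim of improvement would exceed the nominal rate.

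The second worry is the scale's shape. With three grades below 4 and one above it, a few large improvements can outweigh a larger number of worsened subjects in the mean. A reader given only the mean could not tell how many subjects improved or worsened.

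**Working it through.** The plan states no power, alpha or sample-size figure for this test, so there is none of its own to reproduce. The t-test, two-sided 5% level, rating spreads and correlations below are assumptions.

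**1. How many scores exist.** Inputs: 1 on-site clinician, 2 visits, 1 or 2 scored steps per visit (Section 11.4), 3 panel raters, 1 or 2 panel time points (Section 11.10).

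Scores per subject = 2 × steps + 3 × panel time points

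| Steps scored | Panel time points | Total |
|---|---|---|
| 1 | 1 | 2 + 3 = 5 |
| 1 | 2 | 2 + 6 = 8 |
| 2 | 1 | 4 + 3 = 7 |
| 2 | 2 | 4 + 6 = 10 |

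The on-site clinician alone supplies 2 scores, or 4 if each step is scored.

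**2. Which score the text points to.** Section 12 refers to the Clinician's scale. The primary endpoint in Section 6.1 and the assessment in Section 11.4 use that same title word. Section 3 assigns clinician scoring to one unblinded clinician. Section 11.10 uses a differently worded title for the panel's version, though the acronym is shared. Section 6.1 names both visits, and Section 12's general framework covers all applicable post-baseline time points. The natural reading is the on-site clinician's score, tested once at each of two visits.

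**3. False-improvement rate.** Model: 13 subjects; normal latent ratings centred on 4, rounded and capped to grades 1-5; one-sample t-test against 4, critical value t(12) = 2.179; nominal 2.5% toward improvement. Between-visit correlation is 0.5-0.7 and between-rater correlation 0.3-0.7. The share rated worse is P(Z > 0.5/SD): 16% at SD 0.5 and 25% at SD 0.75.

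| What is tested | SD 0.5-0.75 |
|---|---|
| One named score | 2.3-2.4% |
| Either of two visits | 4.2-4.5% |
| Any of 5 scores | 8.6-10.5% |
| Any of 8 scores | 11.9-15.6% |
| Panel pooled as 39 independent ratings | 4.8-11.2% |
| Panel mean per subject | 2.3-2.9% |

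On the natural reading the rate is at most 4.5/2.5 = 1.8 times nominal, and only if a single significant visit is taken as enough.

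The result also depends on the spread. At SD 0.3 (about 5% rated worse), one score gives about 0.2%, either visit 0.3-0.4% and any of 8 scores 1.2-1.3%, all below nominal; pooling 39 ratings still gives 3.2-5.8%. At SD 0.4 (11% rated worse), either visit gives 2.4-2.7% and any of 8 scores 8-9.5%.

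**4. Direction of the mean.** Four subjects rated 2, five rated 4 and four rated 5 give (4×2 + 5×4 + 4×5)/13 = 48/13 = 3.69, with equal numbers improved and worse; t = -0.89, p = 0.39. More extreme: three rated 1, one rated 3 and nine rated 5 give (3 + 3 + 45)/13 = 51/13 = 3.92, below 4 with nine worse and four improved.

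Of all 2,380 ways to spread 13 subjects over five grades, 149 have a mean below 4 with more worse than improved. None with at least as many worse as improved is significant toward improvement. The smallest two-sided p is 0.125 for equal counts (six rated 1, one rated 4, six rated 5) and 0.167 for more worse than improved (six rated 1, seven rated 5).

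**The case for a change.** The strongest case for a change is that the text never excludes the panel's CGAIS from the Section 12 test. Even the on-site reading leaves two visits, and four scores if each step counts. If the choice followed the data, inflation among 5 or 8 scores would be several-fold at SD 0.5-0.75. Naming one score, one visit, a test and an alpha would take two sentences and no new data, and grade counts would show direction plainly.

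Much of this stands as description: the wording is incomplete, the count of available scores is right, and the simulated rates hold under their assumptions. What does not stand is the step to a defect in the plan. Several-fold inflation requires a free choice among raters, or pooled panel ratings, which no section proposes. It also rests on a rating spread that the documents do not give. The consequence is limited too: the study is single-arm and unblinded, with up to 13 subjects, Section 12 calls it initial, and no visible success rule hangs on this test. Section 12 also attaches its primary effectiveness comparison to the instrumental, biopsy and 3D imaging measures. Grade counts are a reporting choice that Section 12 does not prevent.

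**Conclusion.** No change to the plan is needed. Section 12 leaves out detail but does not set a wrong rule. Its null value matches the scale's no-change grade, and an analyst following the document would test the on-site clinician's score, one value per subject, at Month 3 and at Month 6. Each such test runs at about 2.3-2.4% toward improvement against 2.5% nominal when the latent SD is 0.5-0.75, and below nominal when ratings are tightly clustered. Taking either visit as sufficient gives 4.2-4.5% at those spreads.

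The uneven scale is a matter of description: at 13 subjects, no pattern with at least as many worse as improved can reach two-sided 5% significance toward improvement. These conclusions rest on an assumed one-sample t-test at two-sided 5%, 13 evaluable subjects, and the assumed spreads and correlations. They would weaken if the reported test used the panel's ratings as independent observations or a score picked after the fact; nothing in the document indicates either.
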